6.5 Data Summarization and Presentation

All CVN424 PK concentrations and/or PK parameters descriptive statistics will be generated using SAS® Version 9.4 or higher.

The plasma and urine concentrations of CVN424 will be listed and summarized by treatment and time point for all participants in the PK Set. Plasma and urine concentrations of CVN424 will be presented with the same level of precision as received from the bioanalytical laboratory. Summary statistics, including sample size (n), arithmetic mean (mean), standard deviation (SD), coefficient of variation (CV%), standard error of the mean (SEM), minimum, median, and maximum will be calculated for all nominal concentration time points. Excluded participants will be included in the concentration listings, but will be excluded from the summary statistics and noted as such in the tables. All BLQ values will be presented as "BLQ" in the concentration listings and tables but will be set to zero (0) or missing as described in Sections 6.4.1 and 6.4.2, for each matrix and footnoted accordingly.

For urine collected over intervals, only concentration and volume parameters will be presented for the predose collection interval.

Plasma mean and individual concentration-time profiles will be presented on linear and semilog scales. Individual concentration-time profiles will be based on actual sample times, and mean concentration-time profiles will be based on nominal sample times. When there are significant time deviations from nominal sample time points, some concentrations may be excluded from the summary statistics and any corresponding summary figures.

Urine mean cumulative CVN424 excretion profiles will be presented on linear scale. Linear mean plots will be presented with and without SD.

Plasma CVN424 PK parameters, including individual treatment ratios, will be listed and summarized by treatment for all participants in the PK Set. PK parameters will be reported to 3 significant figures for individual parameters, with the exception of C_{max}, which will be presented with same level of precision as received from the bioanalytical laboratory and T_{max}, T_{lag} which will be presented with 2 decimal places. Summary statistics (n, mean, SD, CV%, SEM, minimum, median, maximum, geometric mean (Geom Mean) and geometric CV% (Geom CV%)) will be presented for all PK parameters. Excluded participants will be listed in the PK parameter tables, but will be excluded from the summary statistics and noted as such in the tables.

Urine CVN424 PK parameters will be listed and summarized using descriptive statistics (n, mean, SD, CV%, SEM, minimum, median, and maximum) for the PK Set. Excluded participants will be listed in the urine PK tables, but will be excluded from the summary

statistics and noted as such in the tables. Urine concentrations that are BLQ will be presented as "BLQ" in the listings and treated as zero (0) for the calculation of summary statistics.

The level of precision for each concentration and PK parameter statistic will be presented as follows: minimum/maximum in same precision as in bioanalytical data and/or parameter output, mean/median/Geom Mean in one more level of precision than minimum/maximum, SD/SEM in one more level of precision than mean/median/Geom Mean, n will be presented as an integer, and CV%/Geom CV% will be presented to the nearest tenth.

6.6 Statistical Analysis of PK Parameters

A comparison of the natural-log (ln)-transformed PK parameters AUC_{0-t}, AUC_{0-96h}, AUC_{0-inf} and C_{max} will be made to evaluate the relative bioavailability of CVN424 Tablet-Fasted versus Suspension-Fasted and Table-Fed versus Suspension-Fasted; Tablet-Fed versus Tablet-Fasted for evaluation of the FE by performing an analysis of variance (ANOVA) model using SAS[®] PROC MIXED. The ANOVA model will include treatment, period, and sequence as fixed effects and participant nested within sequence as a random effect. The geometric least squares mean (LSM) values reported in the statistical comparisons will be the exponentiated LSMs from the ANOVA. The geometric ratio of the LSMs will be calculated from the exponentiated difference between the treatment LSMs from the ANOVA analysis. The 90% confidence intervals (CIs) for the ratios will be derived by exponentiation of the CIs obtained for the difference between the treatment LSMs. The CIs will be expressed as a percentage relative to the reference treatment.

The comparisons of interest are as follows:

- BA Assessment:
 - Treatment B (Tablet-Fasted, test) compared with Treatment A (Suspension-Fasted, reference)
 - Treatment C (Tablet-Fed, test) compared with Treatment A (Suspension-Fasted, reference)
- Food Effect (high-fat, high-calorie meal): Treatment C (Tablet-Fed, test) compared with Treatment B (Tablet-Fasted, reference)

Similar BA criteria will be met if the 90% CIs for the ratios of LSMs of In-transformed AUC_{0-t}, AUC_{0-96h}, and C_{max} of CVN424 fall within 80.00 and 125.00% (Tablet- Fasted versus Suspension-Fasted; Tablet- Fed versus Suspension-Fasted).

The lack of a food effect will be concluded if the 90% CIs for the ratios of LSMs of Intransformed AUC_{0-t}, AUC_{0-96h}, and C_{max} of CVN424 fall between 80.00 and 125.00% (Tablet-Fed versus Tablet-Fasted).

The ANOVA analysis will be performed using the following SAS® code:

PROC MIXED;

CLASS TREATMENT PARTICIPANT PERIOD SEQUENCE;
MODEL ln(PK_PARAMETER) = TREATMENT PERIOD SEQUENCE / DDFM=KR;

RANDOM PARTICIPANT(SEQUENCE);

ESTIMATE "Tablet-Fasted vs Suspension-Fasted" TREATMENT -1 1 0 / cl alpha=0.1 e; ESTIMATE "Tablet-Fed vs Suspension-Fasted" TREATMENT -1 0 1 / cl alpha=0.1e; ESTIMATE "Tablet-Fed vs Tablet-Fasted" TREATMENT 0 -1 1 / cl alpha=0.1 e; LSMEANS TREATMENT / cl alpha=0.1; RUN;

Geometric LSMs will be presented in one more precision level than the associated PK parameter. GMRs and 90% CIs will be presented with 2 decimal places and intra-participant CV% will be presented to 2 decimal places.

Nonparametric Analysis

For Tmax and Tlag, nonparametric comparison between treatments B vs A (and C vs B) will be performed using Walsh Averages and Wilcoxon Signed-Rank Test Statistic. The median difference and the 90% CI of the median difference in Tmax and Tlag will be estimated. Significant differences in Tmax and Tlag values for the treatment comparison will be concluded if the resulting p < 0.05.

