2. OBJECTIVES AND ENDPOINTS

Objectives	Endpoints	
Primary		
To determine the relative bioavailability (BA) of 150 mg of CVN424 administered in a single dose of suspension formulation compared to 150 mg tablet	 The relative bioavailability of the CVN424 suspension in the fasted state, and CVN424 tablet formulation in the fasted and fed state based on maximum observed plasma concentration (Cmax), time to reach Cmax (Tmax), and area under the plasma concentration time curve from time 0 to 96 hours (AUC0-96h) which is the primary area PK parameter. The ratio of the pharmacokinetic (PK) parameters between CVN424 suspension and tablet in the fasted and fed state will be calculated and summarized descriptively. In addition, an analysis of variance (ANOVA) on log-transformed PK parameters (AUC0-1, AUC0-96h, Cmax) will be performed. Ratios of geometric means and 90% confidence intervals will be calculated. Tmax will be compared between CVN424 suspension and CVN424 tablet with and without food. 	

Secondary	
To establish the effects of food (FE) on the rate and extent of absorption of CVN424 150 mg tablet when administered in fed conditions compared to administration under fasting conditions.	• The ratio of the PK parameters between CVN424 tablets in the fed and fasted state will be calculated and summarized descriptively. In addition, an analysis of variance (ANOVA) on log-transformed PK parameters (AUC _{0-t} , AUC _{0-96h} , C _{max}) will be performed. Ratios of geometric means and 90% confidence intervals will be calculated. T _{max} and T _{lag} will be compared between CVN424 tablets in the fed and fasted state.
To assess the safety of the tablet under fast and fed conditions and suspension under fast conditions	• Treatment-emergent adverse events (TEAEs) and tolerability as measured by discontinuations (D/Cs) due to adverse event (AE).
Exploratory*	
Explore serum/plasma (e.g., potential characterization of drug metabolites) that may contribute to variability in CVN424.	Potentially characterize metabolic enzyme and transporter polymorphisms.

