14.2 Pharmacokinetic Data Summary Tables and Figures

14.2.1 Plasma CVN424 Tables

Number	Title	Shell
Table 14.2.1.1	Plasma CVN424 Concentrations (ng/mL) Following Administration of 150 mg CVN424 Suspension-Fasted (Pharmacokinetic Set)	CPCONC1
Table 14.2.1.2	Plasma CVN424 Concentrations (ng/mL) Following Administration of 150 mg CVN424 Tablet-Fasted (Pharmacokinetic Set)	CPCONC1
Table 14.2.1.3	Plasma CVN424 Concentrations (ng/mL) Following Administration of 150 mg CVN424 Tablet-Fed (Pharmacokinetic Set)	CPCONC1
Table 14.2.1.4	Plasma CVN424 Pharmacokinetic Parameters Following Administration of 150 mg CVN424 Suspension-Fasted (Pharmacokinetic Set)	CPPAR1
Table 14.2.1.5	Plasma CVN424 Pharmacokinetic Parameters Following Administration of 150 mg CVN424 Tablet- Fasted (Pharmacokinetic Set)	CPPAR1
Table 14.2.1.6	Plasma CVN424 Pharmacokinetic Parameters Following Administration of 150 mg CVN424 Tablet- Fed (Pharmacokinetic Set)	CPPAR1
Table 14.2.1.7	Plasma CVN424 Pharmacokinetic Parameter Ratios: Tablet-Fasted/Suspension-Fasted, Tablet-Fed/Tablet-Fasted, and Tablet-Fed/Suspension-Fasted (Pharmacokinetic Set)	CPR1
Table 14.2.1.8	Statistical Comparisons of Plasma CVN424 Pharmacokinetic Parameters: AUC0-t, AUC0-96h, and Cmax Tablet-Fasted Versus Suspension-Fasted (Pharmacokinetic Set)	CPStat1

Number	Title	Shell
Table 14.2.1.9	Statistical Comparisons of Plasma CVN424 Pharmacokinetic Parameters: AUC0-t, AUC0-96h, and Cmax Tablet-Fed Versus Suspension-Fasted (Pharmacokinetic Set)	CPStat1
Table 14.2.1.10	Statistical Comparisons of Plasma CVN424 Pharmacokinetic Parameters: AUC0-t, AUC0-96h, and Cmax Tablet-Fed Versus Tablet-Fasted (Pharmacokinetic Set)	CPStat1
Table 14.2.1.11	Nonparametric Statistical Comparison of Plasma CVN424 Tmax and Tlag: Tablet-Fasted Versus Suspension-Fasted (Pharmacokinetic Set)	CPStat2
Table 14.2.1.12	Nonparametric Statistical Comparison of Plasma CVN424 Tmax and Tlag: Tablet-Fed Versus Suspension-Fasted (Pharmacokinetic Set)	CPStat2
Table 14.2.1.13	Nonparametric Statistical Comparison of Plasma CVN424 Tmax and Tlag: Tablet-Fed Versus Tablet- Fasted (Pharmacokinetic Set)	CPStat2

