Calculations will use source data in all statistical analysist of PK parameter without prior rounding

Presentation of Data:

- The following PK parameters will be presented in the following order and with following units: AUC_{0-t} (ng*hr/mL), AUC_{0-96h} (ng*hr/mL), and C_{max} (ng/mL).
- If AUC_{0-t} equals AUC_{0-96h}, then only AUC_{0-96h} will be presented.
- n will be presented as an integer (with no decimal);
- Geometric LSM will be presented with 3 significant figures. While, Geometric Mean Ratio, 90% CI and intra-subject CV% will be presented to 2 decimal places.
- Treatment columns will use the short description presented in Section 5 of the SAP.

Source tables will be:

- For Table 11-3, the source table will be 14.2.1.8. Tablet-Fasted is test and Suspension-Fasted is reference.
- For Tables 11-4, the source table will be 14.2.1.9. Tablet-Fed is test and Suspension-Fasted is reference.
- For Tables 11-5, the source table will be 14.2.1.10. Tablet-Fed is test and Tablet-Fasted is reference.

Program: /CAXXXXX/sas_prg/pksas/intext-pk-tables.sas DDMMYYYY HH:MM
Program: /CAXXXXX/sas_prg/pksas/adam intext_pkparam.sas DDMMYYYY HH:MM

In-text Shell CPStat2/ITPStat2 will be in the following RFT format:

Table CPStat2/ITPStat2 Summary of Nonparametric Statistical Comparison of Plasma CVN424 T_{max} and T_{lag}: Tablet-Fasted Versus Suspension-Fasted (Pharmacokinetic Set)

		- Difference Tablet-Fasted - Suspension-Fasted	
Parameter	Median	90% Confidence Interval	p-value
T _{mx}	XXX	-XXXXX-XXXXX	XXXXX
T_{lg}	XXX	-XXXXX-XXXXX	XXXXX

Notes for Generating the Actual Table:

- All statistics will be presented with same precision as defined in post-text shells
- The 90% confidence interval is constructed using Wilcoxon Singed rank test.

Programmer Note:

- For Table 11-6 the source tables will be 14.2.1.11.
- For Table 11-7 the source tables will be 14.2.2.12.
- For Table 11-8 the source tables will be 14.2.2.13.

Program: /CAXXXX/sas_prg/pksas/adam_programname.sas DDMMMYYYY HH:MM

Table IAES Treatment-Emergent Adverse Event Frequency by Treatment- Number of Participants Reporting the Event (% of Participants Dosed) (Safety Set)

		Treatment						
	A	В	C	Overall				
Adverse Event	(N = X)	$(\mathbf{N} = \mathbf{X})$	$(\mathbf{N} = \mathbf{X})$	$(\mathbf{N} = \mathbf{X})$				
Number of Participants With TEAEs	XX (XX%)	XX (XX%)	XX (XX%)	XX (XX%)				
Number of Participants Without TEAEs	XX (XX%)	XX (XX%)	XX (XX%)	XX (XX%)				

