- Comparison of interest for Table 14.2.1.8 is Tablet-Fasted versus Suspension-Fasted; for Table 14.2.1.9 is Tablet-Fed versus Suspension-Fasted, for Table 14.2.1.10 is Tablet-Fed versus Tablet-Fasted.

Program: /CAXXXXX/sas_prg/pksas/stats-tables-mixed.sas DDMMYYYY HH:MM Program: /CAXXXXX/sas_prg/pksas/adam_statsmixed.sas DDMMYYYY HH:MM

Page X of X

Table CPStat2. Nonparametric Statistical Comparison of Plasma CVN424 Tmax and Tlag: Tablet-Fasted Versus Suspension-Fasted (Pharmacokinetic Set)

Difference <x></x>	- <y></y>	
--------------------	-----------	--

Parameter	Median	90% Confidence Interval	p-value
Tmax	X.XX	-x.xxxx - x.xxxx	X.XXXX
Tlag	X.XX	-x.xxxx - x.xxxx	X.XXXX

Treatment <X>: <Label for First Treatment>
Treatment <Y>: <Label for Second Treatment>

Notes for Generating the Actual Table:

Presentation of Data:

- The 90% confidence interval is constructed using Wilcoxon Singed rank test.
- Median difference will be presented to 2 decimals or 3 significant figures
- 90% CI will be presented to 4 decimals
- p-value will be presented to 4 decimals

Programmers Note:

• For Table 14.2.1.11, Tablet-Fasted is the test, Suspension-Fasted is reference. For Table 14.2.1.12, Tablet-Fed is the test, Suspension-Fasted is reference. For Table 14.2.1.13, Tablet-Fed is the test, Tablet-Fasted is reference.

Program: DM PX:[HLXXXXX.PKSAS]XXXX.SAS DDMMMYYYY HH:MM

Table C(A) UPar3 Urinary Excretion of CVN424 Following Administration of 150 mg CVN424 Tablet-Fasted (Pharmacokinetic Set)

Subject Treatment Study Number Sequence Period X XXXX X X XXX X X XXX X X XXX X X XXX X ST X X XXX X ST X X XXX X ST X X X X X X ST X X X X X X X X X X X X X X X X X X X	Conc (units) X.XX X.XX	Predose Vol (units) X.XX	Conc (units)	Vol (units)	Aet1-t2 (units)	Ae (units)	X - fe (%)	- X Hours CLR (units)
Number Sequence Period X XXX X CONTROL OF THE CONTROL OF T	(units) X.XX X.XX	(units) X.XX	(units)	(units)				
X XXX X X XXX X n Mean SD CV%	X.XX		 XX.XX					(311100)
Mean SD CV%	X.XX	X.XX X.XX	XX.XX XX.XX	X.XX X.XX X.XX	X.XX X.XX X.XX	X.XX X.XX X.XX	X.XX X.XX X.XX	X.XX X.XX X.XX
Minimum Median Maximum Geom Mean Geom CV%	X X.XXX X.XXXX X.XX X.XXX X.XXX X.XXX X.XXX	X X.XXX X.XX	X XX.XXX XX.XXX XX.XX XX.XXX XX.XXX XX.XXX XX.XXX XX.XXX	X X.XXX X.XXX X.X X.XXX X.XXX X.XXX X.XXX X.XXX X.XXX	X X.XXX X.XXX X.X X.XXX X.XXX X.XXX X.XXX X.XXX X.XXX	X X.XXX X.XXX X.XX X.XXX	X X.XXX X.XXXX X.X X.XXX X.XXX X.XXX X.XXX X.XXX	X X.XXX X.XXXX X.XX X.XXX X.XXX X.XXX X.XXX X.XXX X.XXX

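### Is the Tablet-Fed versus Suspension-Fasted comparison of Tmax and Tlag left without a planned test because SAP 6.6 does not name it?

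*SAP*

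**What the plan says.** The Nonparametric Analysis paragraph of SAP 6.6 states that "nonparametric comparison between treatments B vs A (and C vs B) will be performed using Walsh Averages and Wilcoxon Signed-Rank Test Statistic". It asks for the median difference with a 90% interval, and a significant difference "will be concluded if the resulting p < 0.05".

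Other parts of the SAP go further. In Section 2 the primary row says that "Tmax will be compared between CVN424 suspension and CVN424 tablet with and without food", which means B vs A and C vs A. Tlag appears there only in the secondary row, for the fed against the fasted tablet. The ANOVA part of 6.6 lists C vs A among its bioavailability comparisons and gives it an ESTIMATE statement. The table list includes Table 14.2.1.12, "Nonparametric Statistical Comparison of Plasma CVN424 Tmax and Tlag: Tablet-Fed Versus Suspension-Fasted", with Table 11-7 as its in-text counterpart. The CPStat2 shell in Section 10.3 adds: "For Table 14.2.1.12, Tablet-Fed is the test, Suspension-Fasted is reference".

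The in-text shell note in Section 10.1 reads: "For Table 11-7 the source tables will be 14.2.2.12".

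**The concern.** Taken alone, the nonparametric paragraph cannot be read as inheriting C vs A from the ANOVA list, because it sets out its own, shorter list. A comparison that Section 2 calls primary then seems to have a table with a p-value column but no named method or decision rule. SAP Section 8 declares only the change to the screen-failure summaries, so the omission is not a declared departure.

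If one analyst followed 6.6 to the letter and another followed the table list, the first would leave Tables 11-7 and 14.2.1.12 blank and the second would print two p-values that 6.6 does not mention. Which statements of a significant Tmax or Tlag difference count as pre-specified would then depend on the section followed. The paragraph also does not say whether the test is two-sided, and it sets a 90% interval beside a 0.05 rule.

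**Working it through.** The plan gives no figure to reproduce here, so the check sets the lists side by side.

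**1. Contrasts named in each place**

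| Source | Tmax B-A | Tmax C-A | Tmax C-B | Tlag B-A | Tlag C-A | Tlag C-B | Total |
|---|---|---|---|---|---|---|---|
| Protocol 5.1 | yes | no | yes | no | no | yes | 3 |
| SAP 2 | yes | yes | yes | no | no | yes | 4 |
| SAP 6.6, nonparametric | yes | no | yes | yes | no | yes | 4 |
| SAP 9.1, 9.2 and CPStat2 shells | yes | yes | yes | yes | yes | yes | 6 |

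The protocol's suspension-tablet Tmax comparison is read as fasted, because its primary endpoint is set in the fasted state.

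Tests named in 6.6: 2 contrasts × 2 parameters = 4. Tests in the tables: 3 × 2 = 6. Difference: 6 − 4 = 2, namely Tmax and Tlag for C vs A. Tables 11-7 and 14.2.1.12 show the same analysis twice, so the gap is one contrast.

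**2. What an analyst needs in order to run C vs A**

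- Parameters: Tmax and Tlag, from the titles of Tables 11-7 and 14.2.1.12.
- Test and reference: tablet fed against suspension fasted, from the CPStat2 note in Section 10.3.
- Interval: 90%, signed-rank, from the same shell.
- p-value: a column in the shell, to 4 decimals.
- Method: signed-rank with Walsh averages, in 6.6. The SAP has no other nonparametric method.
- Decision rule: p < 0.05, worded in 6.6 for the treatment comparison in general.

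Nothing is missing once the SAP is read as a whole. Adding C vs A to the 6.6 sentence would give the same two rows of results.

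The appended statistical outputs point the same way. Their 13-page numbering appears to restart about six times, with C vs B footers in what look like the third and sixth runs. That would fit 3 contrasts × 2 parameters = 6. The page contents are not in the available text, so this is only suggestive.

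**3. What depends on the result**

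The 6.6 criteria for similar bioavailability and for no food effect require 90% intervals within 80.00 to 125.00% for AUC0-t, AUC0-96h and Cmax. Neither uses Tmax or Tlag.

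**4. The smaller points**

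- Section 14.2.2 holds only Figures 14.2.2.1 to 14.2.2.6, so 14.2.2.12 and 14.2.2.13 cannot be the sources of Tables 11-7 and 11-8. The same note gives 14.2.1.11 correctly for Table 11-6, and Section 10.3 has 14.2.1.12 and 14.2.1.13. This is a slip of one digit, and SAP 9.2 allows renumbering.
- The rule speaks of significant differences without a direction, and nothing suggests a one-sided test.
- When 0.05 ≤ p < 0.10, a 90% interval can exclude zero beside a non-significant p-value. The SAP says that the p-value decides, so the conclusion is not in doubt.

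**The case for a change.** The strongest case for acting is that a pre-specified analysis should not have to be pieced together from table shells, least of all for a comparison labelled primary, when the repair is one sentence and two table numbers.

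The inconsistency does stand, as does the fact that Section 8 is silent on it. The primary label is weaker than it looks. It comes from SAP Section 2 alone. The protocol's Tmax contrasts are B vs A and C vs B, exactly the pairs in 6.6. On contrasts, 6.6 therefore agrees with the protocol and Section 2 is the extension. Tlag for C vs A rests on the table plan only. SAP Section 1 already sends changes from the protocol's planned analysis to the study report.

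The stake can be given numbers, but not firm ones. Assume 28 pairs, exact two-sided signed-rank tests and normal data without ties. C vs A is then the only Tmax contrast below 0.05 in about 3% of trials with no difference. The share is about 29% if formulation and food each shift Tmax the same way by 0.3 SD of the paired difference. With no formulation shift and a food shift of 0.8 SD it is 1.7%. The documents give no SD for Tmax, and sampling every half hour up to 2 hours makes ties likely, so nothing anchors a value in that range. These figures also matter only if C vs A were skipped, which the shells make unlikely.

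The number of unadjusted tests is a separate matter. The tables already plan six, and naming C vs A in 6.6 would not reduce that.

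**Conclusion.** This is a gap that analysts fill sensibly, with a clerical slip beside it. One contrast, giving 2 of 6 planned p-values, is missing from the method sentence but fully specified by the table list, the shell and the general rule in the same SAP. The same test would be run and the same numbers printed with or without an edit, and no conclusion on AUC, Cmax, relative bioavailability or food effect would move. This rests on two assumptions: that the analyst works from the whole SAP, shells included, and that the signed-rank test is two-sided, as the wording of its rule implies.

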6.7 Interim Analysis

Interim analysis will be conducted for plasma data in Period 1, 2 and 3 and details of the interim analysis are described in a separate document.

7. SAFETY

All safety data will be listed by participant and chronologically by assessment time point. This will include rechecks, unscheduled, and early termination assessments. Data for participants who screen failed will be listed in separate appendices.

Applicable continuous variables will be summarized using n, mean, SD, minimum, median, and maximum.

The level of precision will be presented as follows: minimum/maximum in the same precision as in the database, mean/median in one more precision level than minimum/maximum, SD in one more precision level than mean/median, and n will be presented as an integer. Percentages will be presented as an integer.

Where individual data points are missing because of dropouts or other reasons, the data will be summarized based on reduced denominators.

Baseline will be the result closest and prior to the dose in the respective period unless otherwise stated. Summaries for post-baseline time points will not include rechecks, unscheduled, or early termination measurements.

Tables summarizing safety data by assessment time point will only include summaries for baseline and post-baseline time points.

7.1 Participant Disposition

Participants will be summarized by the number and percent of participants dosed, completed the study, discontinued the study (with discontinuation reasons), completed treatment, and discontinued from treatment (with treatment discontinuation reasons) by randomized treatment sequence and overall.

Individual participant dosing status (i.e., which treatments were administered to each participant) will also be provided along with their study completion status and date of study completion or discontinuation. The number of participants dosed for each treatment will also be presented.

